Bleeding was not observed more frequently in selexipag-treated patients compared to placebo, including in those patients treated concomitantly with anticoagulants. Anemia was reported more frequently in the selexipag group and a small reduction in hemoglobin was observed at most post-baseline visits.

Hyperthyroidism was reported more frequently in the selexipag group than in the placebo group. The corresponding laboratory changes were small reductions in thyroid-stimulating hormone (TSH) at most post-baseline visits. A possible association between thyroid disorders and PAH is described in the literature [[Marvisi 2013](#)]. Previously published investigations showed that prostaglandins may influence thyroid function by a direct effect on specific prostaglandin membrane receptors [[Chadha 2009](#)].

Other AEs included nasopharyngitis (very common); decreased appetite, weight decreased, nasal congestion, rash, urticaria, erythema, abdominal pain, and pain (all reported as common).

Importantly, there were no additional safety and tolerability findings in the GRIPHON study in those patients receiving selexipag on top of both an ERA and a PDE-5 inhibitor.

Safety data from other completed selexipag clinical studies in adult patients with PAH, CTEPH, Raynaud's Phenomenon secondary to SSc, and ASO-IC show a safety profile consistent with that of the GRIPHON study [[Selexipag IB](#)]. Safety data in this study are

reviewed on an ongoing basis by the Independent Data Monitoring Committee (IDMC) (see Section 3.3).

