### C) Hyperthyroidism

Hyperthyroidism has been observed in 1% of the participants treated with selexipag in the GRIPHON study [Uptravi® USPI, Uptravi® SmPC].

The investigator is asked to inform the participants and the parents and provide guidance that they should be proactive and report if, at any time during study treatment, the participant experiences clinical signs of hyperthyroidism (eg, sudden weight loss even if appetite and the amount and type of food remain the same or even increased), tachycardia, arrhythmia or palpitations, nervousness, anxiety and irritability, tremor, sweating, an enlarged thyroid gland, difficulty sleeping).

If the participant experiences new or worsening of pre-existing hyperthyroidism during the course of treatment with study medication that, in the opinion of the investigator, cannot be adequately controlled with anti-thyroid medications, the study drug must be permanently discontinued and the participant monitored until resolution of this condition.

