### 6.2 Safety endpoints

- Treatment-emergent AEs (TEAEs) occurring up to EOT + 3 days.
- Treatment-emergent SAEs (TESAEs) occurring up to EOT + 3 days.
- AEs leading to permanent discontinuation of study drug.
- Treatment-emergent deaths (all causes) occurring up to EOT + 3 days.
- Treatment-emergent marked laboratory abnormalities (hematology and blood chemistry tests) over time occurring up to EOT + 3 days.
- Change from baseline in selected hematology and blood chemistry laboratory variables over time up to EOT + 3 days.
- Treatment-emergent ECG abnormalities over time occurring up to EOT + 3 days.
- Change from baseline in TSH over time up to EOT + 3 days.
- Change from baseline in vital signs (blood pressure, heart rate) over time up to EOT + 3 days.
- Change from baseline in height and body mass index over time up to EOT + 3 days.
- Change from baseline in sexual maturation (Tanner stage) over time up to EOT + 3 days.

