4.2. Clinical Laboratory Tests

The following laboratory parameters are evaluated:

- Hematology:
 - Hemoglobin (g/L)
 - Hematocrit (L/L)
 - Erythrocyte count ($10^9/L$)
 - Leukocyte count with differential counts ($10^9/L$)
 - Platelet count ($10^9/L$)
- Clinical chemistry:
 - Alanine aminotransferase (U/L)
 - Aspartate aminotransferase (U/L)
 - Alkaline phosphatase (U/L)
 - Total and direct bilirubin ($\mu\text{mol/L}$)
 - Creatinine ($\mu\text{mol/L}$)
 - Creatinine clearance (mL/min)
 - Serum urea nitrogen (mmol/L)
 - Uric acid ($\mu\text{mol/L}$)
 - Glucose (mmol/L)
 - Cholesterol, triglycerides (mmol/L)
 - Sodium, potassium, chloride, calcium (mmol/L)
 - Albumin (g/L)
 - NT-pro BNP (pmol/L)
 - TSH (mU/L)
 - Free T3 and free T4 (pmol/L)
 - Thyroid antibodies (U/mL)

In addition, local laboratory parameters might be available under certain circumstances and recorded in the CRF.

All recorded assessments, whether from central or local laboratory (including unscheduled) will be assigned to the most appropriate visit time points according to the best fitting time-window for that assessment

If data from a local laboratory and from the central laboratory are available for the same date, the central laboratory value will be used; if more than one valid assessment are available on the same timepoint window in the same lab, the mean value will be considered.

A laboratory test abnormality is defined as any value outside the normal range as provided by the laboratory. The direction of the abnormality (below or above the normal range) is indicated using 'H' and 'L', if applicable.

A marked (alert) laboratory test abnormality is defined as any value that fulfills the applicable condition listed in the table below for LL / HH (or LLL / HHH, respectively):

Safety parameter	Marked Abnormally Low Values		Marked Abnormally High Values	
	LL	LLL	HH	HHH
Hematology				
Hemoglobin (g/L)	< 100	< 80	Increase (> 20 g/L) above ULN or above baseline if baseline is above ULN	Increase (> 40 g/L) above ULN or above baseline if baseline is above ULN
Hematocrit (L/L)	< 0.28 F < 0.32 M	< 0.20	> 0.55 F > 0.60 M	> 0.65
Erythrocyte count (10 ⁹ /L)	NA	NA	NA	NA
Leukocyte count with differential counts (10 ⁹ /L)	< 3.0	< 2.0	> 20.0	> 100.0
Platelet count (10 ⁹ /L)	< 75	< 50	> 600	> 999
Clinical chemistry				
AST (U/L)	NA	NA	> 3 ' ULN	> 5 ' ULN
ALT (U/L)	NA	NA	> 3 ' ULN	> 5 ' ULN
Alkaline phosphatase (U/L)	NA	NA	> 2.5 ' ULN	> 5 ' ULN
Total bilirubin (µmol/L)	NA	NA	> 2 ' ULN	> 5 ' ULN

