Direct bilirubin (µmol/L)	NA	NA	> 2 ' ULN	> 5 ' ULN
Creatinine (µmol/L)	NA	NA	> 1.5 ' ULN or > 1.5 ' baseline if baseline is above ULN	> 3 ' ULN or > 3 ' baseline if baseline is above ULN
Serum urea nitrogen	NA	NA	> 2.5 x ULN	> 5 x ULN
Glucose (mmol/L)	< 3.0	< 2.2	> 8.9	> 13.9
Sodium (mmol/L)	NA	< 130	> 150	> 155
Potassium (mmol/L)	< 3.2	< 3.0	NA	> 6.0
Calcium (mmol/L)	< 2.0	< 1.75	> 2.9	> 3.1

ALT = alanine aminotransferase; AST = aspartate aminotransferase; F = female; M = male; ULN = upper limit of normal range.

Treatment-emergent marked laboratory abnormalities are defined as all marked laboratory abnormalities with onset after the study treatment start and up to EOT+3 days, that were not present at baseline or worsened during the course of the study. They will be analyzed on the Safety Analysis Set overall, by age cohort and body weight group.

For each category (i.e., LL, LLL, HH, HHH), treatment-emergent marked laboratory abnormalities are summarized for each laboratory variable overall, by age cohort and body weight group, displaying counts and percentages of participants with at least one marked treatment-emergent abnormality. Percentages are calculated by dividing the number of participants with at least one marked abnormality for the parameter under consideration by the number of participants with any post-baseline measurement.

The number of participants with laboratory abnormalities/marked abnormalities (any value outside the normal ranges for the laboratory) will be also tabulated as shift tables against baseline.

Absolute values and changes from baseline will be determined for each parameter and participant at the different timepoints of assessment and summarized overall, by age cohort and body weight group for the Safety Analysis Set. For graphs or tables with mean values, to account for changing reference ranges across age and gender, certain central and local laboratory values (Y_{ori}) and their reference ranges (LLN_{ori} , ULN_{ori}) will be normalized as Y_{norm} using a standard range (LLN , ULN) as follows:

$$Y_{norm} = LLN + \frac{(Y_{ori} - LLN_{ori})}{(ULN_{ori} - LLN_{ori})} \times (ULN - LLN)$$

If the value is negative after normalization, zero will be assigned.

The laboratory tests that require normalization and their standard ranges to be used are:

- TSH: 0.34 - 5.60 (mIU/L)
- Free T3: 4.5 - 7.8 (pmol/L)
- Free T4: 10 - 24 (pmol/L)
- Hemoglobin: 116 - 164 (g/L)
- Hematocrit: 0.34 - 0.48 (L/L)

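### Setting negative normalised laboratory values to zero can shorten the recorded fall in TSH when the laboratory's upper-to-lower limit ratio is below about 16.5

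*SAP*

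**What the plan says.** SAP 4.2 introduces the rescaling with "For graphs or tables with mean values, to account for changing reference ranges across age and gender, certain central and local laboratory values". A value Y from a laboratory with limits L and U becomes LLN + (Y - L)/(U - L) × (ULN - LLN), where LLN and ULN are the SAP's standard limits, 0.34 and 5.60 mIU/L for TSH. The next sentence reads "If the value is negative after normalization, zero will be assigned". It covers every normalised test and makes no exception for TSH.

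Protocol 6.2 names the safety endpoint "Change from baseline in TSH over time up to EOT + 3 days", and Protocol 10.3.5.3 plans a summary of it over time. The background on the adult trial (Protocol 1.2.3.4.2) reports more hyperthyroidism on selexipag and adds: "The corresponding laboratory changes were small reductions in thyroid-stimulating hormone (TSH) at most post-baseline visits".

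The marked-abnormality table in SAP 4.2 has no TSH row. SAP 4.3 promises a separate thyroid presentation but does not say whether it uses raw or normalised values.

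**The concern.** One zero rule serves tests whose standard ranges sit at very different distances from zero. For hemoglobin and platelets the floor lies far below the normal range. For TSH it lies just below it, because 0.34 is a small fraction of the range width.

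The rule can remove only low values, and low is the direction of the known drug signal. It therefore shortens the recorded fall of a strongly suppressed child and never lengthens it. With no marked-abnormality row for TSH, no tabulated count grades the depth of suppression. The shift tables place any value below the laboratory's limit in one category, so the mean-value tables are the main summary in which depth could show.

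**Working it through.** **Inputs from the SAP.** Standard TSH range 0.34-5.60 (width 5.26); hemoglobin 116-164 (width 48); platelets 140-400 (width 260); the linear formula and the zero rule.

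**Input not in the documents.** The laboratory's own TSH limits by age and sex. The SAP refers only to the range that the laboratory supplies ("A laboratory test abnormality is defined as any value outside the normal range as provided by the laboratory"). The ranges used below are assumptions.

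**Where the floor starts.** Setting the normalised value to zero gives the cut-off

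Y* = L - (0.34/5.26) × (U - L) = L - 0.0646 × (U - L).

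The same margin is 116/48 = 2.4 range-widths for hemoglobin and 140/260 = 0.54 for platelets.

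As a fraction of the laboratory's lower limit, Y*/L = 1 - 0.0646 × (U/L - 1). This is above zero only when U/L is below 5.60/0.34 = 16.47.

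**One range worked through (assumed 0.6-4.8).** Cut-off: 0.6 - 0.0646 × 4.2 = 0.329, or 55% of 0.6. A TSH of 0.01 normalises to 0.34 + (0.01 - 0.6)/4.2 × 5.26 = -0.399, recorded as 0. A baseline of 2.5 normalises to 2.720. The fall is 3.118 without the floor and 2.720 with it, so 1 - 2.720/3.118 = 12.8% is lost.

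**All ranges, for a fall to 0.01 mU/L.**

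| Laboratory range | U/L | Cut-off (mU/L) | Cut-off as % of L | Fall lost from 2.5 | Fall lost from 1.0 |
|---|---|---|---|---|---|
| 0.34-5.60 (SAP standard) | 16.5 | 0 | 0% | 0% | 0% |
| 0.4-4.5 (assumed) | 11.3 | 0.135 | 34% | 5% | 13% |
| 0.5-4.3 (assumed) | 8.6 | 0.254 | 51% | 10% | 25% |
| 0.6-4.8 (assumed) | 8.0 | 0.329 | 55% | 13% | 32% |
| 0.7-6.0 (assumed) | 8.6 | 0.357 | 51% | 14% | 35% |
| 0.9-6.5 (assumed) | 7.2 | 0.538 | 60% | 21% | 53% |

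Other assumed ranges widen the spread: 0.35-5.5 gives a cut-off of 5% of the lower limit and 0.7-4.2 gives 68%.

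**Effect on a cohort mean.** Per suppressed value, the most that can be removed (raw TSH near zero) is 5.26/(U/L - 1) - 0.34. That is 0.17 at U/L = 11.3 and 0.51 at U/L = 7.2. Taking 0.35 as a middle figure, one suppressed child among 20 moves the mean change by 0.35/20 = 0.018 mIU/L, and one among 60 by 0.35/60 = 0.006. With 10% of children suppressed the shift is 0.035.

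**Effect on the extremes.** SAP 7 includes the minimum, maximum and quartiles in continuous summaries. SAP 4.2 rescales the values that feed tables containing means, not just the mean itself. On that reading the smallest TSH shown cannot go below zero on the normalised scale, and the largest fall is shortened even if only one child is affected.

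**The case against.** The strongest reply is that little is lost and the rest is visible elsewhere.

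- **The cut-off is not a documented figure.** A reader might infer that TSH is truncated at a third to 60% of the lower limit. The documents do not support that as a fact: it follows only from assumed ranges, and at the one TSH range they print the cut-off is zero. This stands.
- **The fall is not hidden.** A reader might infer that the TSH signal disappears, or that a mildly and a fully suppressed child become indistinguishable. Neither follows. Only the part of a fall below the cut-off is lost, and values between the cut-off and the lower limit keep their own normalised value. The 53% figure needs the most extreme pairing tried.
- **The adult signal was small.** Small falls that stay above the cut-off are untouched. Protocol 5.1.10 says "Hyperthyroidism has been observed in 1% of the participants treated with selexipag in the GRIPHON study"; at that rate, fewer than one case would be expected among about 60 children. A median also hardly moves when a few low values are floored.
- **Other outputs are intact.** The rescaling is confined to displays of means. Low flags and shift tables use the laboratory's own range, individual values are listed, and the hyperthyroidism AESI includes a decreased-TSH term.
- **The yardstick is debatable.** The unfloored value is a negative TSH, which is an artefact of linear rescaling. From 2.5 to 0.01 the raw fall is 2.49. The floored normalised falls are 3.03, 3.11 and 2.72 in three of the assumed ranges, larger than the raw fall, and 2.13 and 1.84 in the other two.

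The last point shows that the percentages describe loss on the SAP's own normalised scale, not loss of measured mU/L. It does not rescue the rule. That scale expresses change in range-widths, and the floor breaks it at the low end, at a raw TSH that depends on each child's range.

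**Conclusion.** The point holds in a limited, conditional form. The zero rule shortens the recorded TSH fall of strongly suppressed children when the laboratory's U/L is below about 16.5, and it acts only in the direction of the known drug signal. Under the five assumed ranges, the loss for a fall to 0.01 mU/L is about 5-21% from a baseline of 2.5 and 13-53% from 1.0. The minimum and largest fall in the mean-value tables are affected as well, if every statistic in those tables uses normalised values.

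A reader might infer that the cohort-level TSH result is materially biased. The arithmetic does not support that: the shift in a mean is a few hundredths of a mIU/L or less unless several children are suppressed. This is a small reporting defect in the summary of a named safety endpoint. Its size cannot be settled without the laboratory's ranges.

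**What to change.** Make one of two changes in the SAP:

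1. In SAP 4.2, exempt TSH from the zero rule and keep negative normalised values. The cost is one sentence, one programming line and a footnote explaining negative values.
2. In SAP 4.3, state that the TSH summaries of values and of change from baseline use the unnormalised scale and include the median and minimum. The cost is one sentence and at most one extra table.

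Either is sufficient and neither needs new data. Quoting the laboratory's TSH ranges by age and sex would also let a reader see whether the floor acts at all. A geometric mean ratio to baseline would be a reasonable addition on the raw scale, but it is optional.

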4.3. TSH, Thyroid antibodies and T3 and T4

In addition, TSH (mU/L), thyroid antibodies (U/mL), free T3 (pmol/L) and free T4 values (pmol/L) will be presented separately.

4.4. Pregnancy Test

Serum pregnancy test will only be performed at screening. Afterwards urine pregnancy test will be performed. All results, as recorded in the eCRF, will be listed.

4.5. Electrocardiograms

ECG will be evaluated by a central ECG service. All ECG data from scheduled and unscheduled visits will be listed.

The quantitative ECG variables up to EOT + 3 days that will be summarized are heart rate (bpm), RR interval (msec), PR interval (msec), QRS interval (msec), QT interval (msec), QTcB (msec) and QTcF (msec), the corrected QT (QTc) using Bazett's and Fridericia's methods, respectively. Values at all scheduled visits and changes from baseline (last value assessed before first study dose intake) over time will be summarized by parameter, time point, age cohort and body weight, and will be presented in figures as well.

In addition, QTcB and QTcF will also be summarized by age cohort and the following categories:

- Value ≤ 450 (normal)
- Value $> 450 - \leq 480$
- Value $> 480 - \leq 500$
- Value > 500
- Increase from baseline ≤ 30
- Increase from baseline $> 30 - \leq 60$
- Increase from baseline > 60
- Value > 480 and increase from baseline $> 30 - \leq 60$
- Value > 480 and increase from baseline > 60

For Week 1 and Week 12, where two additional ECG assessments are done at 2H and 4H post-dose, only pre-dose data will be included in the overall analysis. In addition, separate analyses will be done with only Week 1 and Week 12 ECGs data, where values and change from pre-dose to post-dose at each visit will be summarized by parameter, abnormality category for QTcB/F, time

point, and age cohort. Furthermore, summary of QTcF/B abnormalities by category over time and shift tables will be provided for both the overall analysis and Week 1 & 12-focused analysis.

The qualitative ECG abnormal findings at study baseline will be summarized by age cohort and are defined as following:

- Atrioventricular Conduction - 1st Degree Av Block
- Chamber Hypertrophy or Enlargement - Left Atrial Abnormality
- Chamber Hypertrophy or Enlargement - Left Ventricular Hypertrophy
- Chamber Hypertrophy or Enlargement - Right Atrial Abnormality
- Chamber Hypertrophy or Enlargement - Right Ventricular Hypertrophy
- Interpretation - Abnormal
- Interpretation - Not Evaluable
- Intraventricular-Intraatrial Conduction - Incomplete Right Bundle Branch Block
- Intraventricular-Intraatrial Conduction - Intraventricular Conduction Delay, Nonspecific
- Intraventricular-Intraatrial Conduction - Left Posterior Fascicular Block
- Intraventricular-Intraatrial Conduction - Right Bundle Branch Block
- ST Segment, T wave, and U wave - QTc Prolongation
- ST Segment, T wave, and U wave - ST Depression
- ST Segment, T wave, and U wave - T Wave Inversion
- Sinus Node Rhythms and Arrhythmias - Sinus Bradycardia
- Sinus Node Rhythms and Arrhythmias - Sinus Tachycardia
- Supraventricular Arrhythmias - Ectopic Atrial Rhythm

Treatment-emergent qualitative ECG abnormalities, defined as any ECG abnormal finding assessed up to EOT + 3 days and reported by the central ECG reader that was not present at study baseline (last assessment before first study drug intake), will also be summarized by age cohort. ECG abnormalities will be also presented in figures.

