### 1.2.3.2 Pharmacokinetics and metabolism

The pharmacokinetics (PK) of selexipag and its active metabolite ACT-333679 were dose-proportional up to a single dose of 800 µg and multiple doses of up to 1,800 µg b.i.d. Steady-state conditions of selexipag and its active metabolite were reached within 3 days. No accumulation in plasma was observed.

Selexipag is rapidly absorbed and is hydrolyzed by carboxylesterase (CES) enzymes to its active metabolite. Maximum observed plasma concentrations of selexipag and its active metabolite after oral administration are reached within 1-3 hours and 3-4 hours, respectively. Oxidative metabolism primarily catalyzed by cytochrome P450 (CYP) 2C8 and to a smaller extent by CYP3A4 leads to the formation of hydroxylated and dealkylated products. Uridine 5'-diphosphoglucuronosyltransferase (UGT) 1A3 and UGT2B7 are involved in the glucuronidation of the active metabolite. Except for the active metabolite, none of the circulating metabolites in human plasma exceed 3% of the total drug-related material [[Selexipag IB](#), Section 5.2.2]. After oral administration, exposure at steady-state to the active metabolite in both healthy subjects and patients with PAH is approximately 3- to 4-fold higher than to the parent compound. In the presence of food, the exposure to selexipag after a single dose of 400 µg was increased by 10% in Caucasian subjects and decreased by 15% in Japanese subjects, whereas exposure to the active metabolite was decreased by 27% (Caucasian subjects) and 12% (Japanese subjects). In the presence of food, the time to reach maximum plasma concentration ( $t_{max}$ ) of selexipag was delayed by approximately 1-1.5 h. More subjects reported adverse events (AEs) after administration in the fasted than in the fed state. Elimination of selexipag is predominantly via metabolism with a mean terminal half-life of 0.8-2.5 h. The active metabolite has a half-life of 6.2-13.5 h. The total body clearance of selexipag is, on average, 17.93 L/h. Excretion in healthy subjects was complete 5 days after administration and occurred primarily via feces (accounting for 93% of the administered dose) compared to 12% in urine. The absolute bioavailability of selexipag is approximately 49%.

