2.4. Baseline Definition

Baseline: Baseline will be defined as the last non-missing assessment available prior to the first dose administration. Any unscheduled measurement performed before administration of study drug should also be used for determination of baseline across all the domains, as some tests may be repeated for confirmation.

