7. STATISTICAL METHODS, CONVENTIONS FOR DISPLAYS AND DECIMAL PRECISION

Unless otherwise specified, all listings will be provided by center and participant number within each age cohort. They will be sorted then by assessment date as appropriate.

Descriptive summary statistics will be provided in the overall population, by age cohort and body weight group.

In summaries for categorical data all participants in the analysis set will be accounted for with tables displaying the number of participants with missing data. The number and percentage of participants in each category will be tabulated by visit as a shift table against baseline.

Summaries for continuous variables will include basic descriptive statistics: mean, median, first and third quartiles, standard deviation and range (minimum and maximum). Mean and median will be displayed as 1 decimal place more than the individual values. The standard deviations (SDs) will be displayed as 1 additional decimal place beyond that of the mean. If a count is 0, the percentage (0%) should not be displayed. The 0 count will be displayed, but the corresponding percentage should be omitted. If the corresponding denominator for the count is also 0, a hyphen (-) should be displayed rather than a 0 count or NA, and the corresponding percentage should be omitted.

- The participant percentages (%) presented in tables will be 1 decimal place unless the sample sizes for the percentages are small enough to warrant presenting as integers. The standard SAS rounding option will be used. For those percentages that rounds to 0.0, along with the count > 0, we will display < 0.1. For those percentages that would round to 100.0, where the count is less than the denominator, we will display > 99.9.
- All dates to be presented in Date9. format, along with time, wherever applicable.

Handling of Missing or Incomplete Date and Time Fields

Conventions for handling incomplete and missing dates are provided below. ‘Lower limit’ and ‘upper limit’ refer to the minimum or maximum, respectively, of a possible date. For example, if the day is missing, the lowest limit is the first day of the given month and the upper limit is the last day of the given month. If the day and month are missing, the lower limit refers to the 1st January of the given year and the upper limit to the 31st December of the given year.

Type of Date	Date is incomplete	Date is missing
Date of PAH diagnosis	Lower limit	No replacement

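### SAP 4.5 plans no quantitative ECG change from the off-drug baseline at 2 h and 4 h post-dose, and leaves open which baseline the Week 1 and Week 12 QTc increase categories use

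*SAP*

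**What the plan says.** SAP 4.5 summarises heart rate, RR, PR, QRS, QT, QTcB and QTcF as values and as "changes from baseline (last value assessed before first study dose intake) over time". For Week 1 and Week 12, where ECGs are also recorded 2 h and 4 h after the dose, "only pre-dose data will be included in the overall analysis". A separate analysis covers those two visits, "where values and change from pre-dose to post-dose at each visit will be summarized by parameter", by QTcB/QTcF abnormality category, time point and age cohort.

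The same section lists QTc categories by absolute value and by increase, ending with "Value > 480 and increase from baseline > 60". It adds that category summaries over time and "shift tables will be provided for both the overall analysis and Week 1 & 12-focused analysis".

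Two general rules bear on how this is read. SAP 2.4: "Baseline will be defined as the last non-missing assessment available prior to the first dose administration". SAP 7 says categorical data "will be tabulated by visit as a shift table against baseline". SAP 4.5 also counts qualitative findings as treatment-emergent when they were absent at study baseline; its list of findings includes QTc prolongation.

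Protocol 7.2.3.3 places the standard ECG before the morning dose and adds the 2 h and 4 h recordings at Visit 3 or Visit 7, whichever is the participant's PK profile visit.

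**The concern.** Protocol 7.2.3.3 puts every other on-treatment ECG before the morning dose, so the planned quantitative change-from-baseline display describes trough. The only near-peak recordings are contrasted with a trough value from the same morning. Notes b and d to protocol Table 4 require at least 3 days on the same dose at the profile visit, and protocol 1.2.3.2 says steady state is reached within 3 days, so that trough is an on-drug value. Any part of an effect already present at trough is subtracted out.

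The increase categories matter most here, because they exist to count individual children above 30 or 60 msec. If one programmer measures the increase from study baseline and another from visit pre-dose, the same ECGs can give different counts. Treatment-emergent ECG abnormalities are a named safety endpoint (protocol 6.2), and this is the first selexipag study in children with PAH (protocol 1.4.3). The 2-4 h window also matters beyond QTc: protocol 1.2.3.4.2 reports a transient mean heart-rate rise of 3-4 beats per minute in that window in the adult pivotal trial.

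**Working it through.** **Which comparisons use the 2 h and 4 h ECGs**

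| Planned output | Reference | Includes 2 h / 4 h? |
|---|---|---|
| Quantitative change over time | Study baseline | No |
| Quantitative change, Week 1 and 12 | Visit pre-dose | Yes |
| Absolute values, Week 1 and 12 | None needed | Yes |
| QTc increase categories and shift tables, Week 1 and 12 | Not settled by the text | Yes |
| Treatment-emergent qualitative findings | Study baseline | No exclusion stated |

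The empty cell is quantitative change from study baseline at 2 h and 4 h.

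On the fourth row the wording points both ways. The list says increase from baseline, and both SAP 2.4 and SAP 4.5 define baseline as the last value before first dose. But the sentence introducing the Week 1 and 12 analysis attaches the abnormality category to the pre-to-post change.

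**How much the reference could matter**

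The plan gives no figure to reproduce, so this is illustrative. Inputs from protocol 1.2.3.2: "The active metabolite has a half-life of 6.2-13.5 h", with peak at 3-4 h; selexipag has a half-life of 0.8-2.5 h and peaks at 1-3 h. The dosing interval is 12 h.

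Assumptions: mono-exponential decline from peak to next dose, and an ECG effect linear in concentration without delay. Then

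- trough/peak = 2^(-(12 - tmax)/half-life)
- share of the peak effect seen in the pre-to-post change = 1 - trough/peak

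| Driver | Half-life (h) | tmax (h) | Trough/peak | Share captured |
|---|---|---|---|---|
| Metabolite | 6.2 | 3 | 0.366 | 0.634 |
| Metabolite | 6.2 | 4 | 0.409 | 0.591 |
| Metabolite | 13.5 | 3 | 0.630 | 0.370 |
| Metabolite | 13.5 | 4 | 0.663 | 0.337 |
| Selexipag | 0.8 | 1 or 3 | 0.000 | 1.000 |
| Selexipag | 2.5 | 1 | 0.047 | 0.953 |
| Selexipag | 2.5 | 3 | 0.082 | 0.918 |

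Example: a child whose QTc is truly 65 msec above the off-drug value at peak belongs in the class above 60. Measured from visit pre-dose, the increase would be 0.337 × 65 = 21.9 to 0.634 × 65 = 41.2 msec if metabolite-driven, which falls in one of the two lower classes. If selexipag-driven it would be 0.918 × 65 = 59.7 to 65 msec.

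**Check on the inputs**

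The same mono-exponential model implies an accumulation ratio of 1/(1 - 2^(-12/half-life)): 1.35 at 6.2 h and 2.17 at 13.5 h. Protocol 1.2.3.2 says no accumulation was observed. The long half-life rows, which give the largest understatement, therefore fit the protocol poorly.

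**What the planned tables can recover**

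In the same participants, mean change from baseline at peak equals mean pre-dose change from baseline plus mean pre-to-post change. Means can be rebuilt that way. The number of children above 30 or 60 msec cannot be rebuilt from means.

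**The case against.** A reader might infer that the near-peak ECGs are never set against an off-drug value and that large increases will therefore be undercounted. The documents do not support this. SAP 4.5 plans absolute post-dose values, whose categories need no baseline. It plans category and shift tables for the Week 1 and 12 analysis, and on the SAP's own definition of baseline those would use the off-drug value. Where the SAP means the same-visit reference, it says pre-dose. Treatment-emergent findings are judged against study baseline with no stated exclusion of post-dose recordings, and all ECGs are listed. This part of the objection stands: undercounting follows only if the increase is read as measured from visit pre-dose.

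It also stands that the size is uncertain. The metabolite is modelled with two compartments (protocol 10.3.2.3), so applying a terminal half-life from peak overstates trough. The absence of accumulation points the same way, and for selexipag the loss is small. Protocol 1.2.3.2 reports no effect on repolarization in healthy subjects at 800 and 1,600 µg b.i.d. With no effect, nothing is understated.

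Finally, same-day pre-dose is a sensible reference in its own right: it limits drift over up to 12 weeks in a single-arm study. The Day 1 ECG is not tied to a clock time, and the first dose is given that evening, so it need not match the morning recordings. This is a reason to keep the planned contrast. It does not replace the missing one.

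**Conclusion.** The point holds as a gap and an ambiguity. No quantitative ECG change from study baseline is specified at 2 h or 4 h, and the baseline for the Week 1 and 12 increase categories and shift tables is not stated clearly enough to program one way.

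The consequence is conditional. If an effect on QTc, heart rate, PR or QRS exists and persists at trough, the pre-to-post change would show about 34%-63% of a metabolite-driven peak effect and about 92%-100% of a selexipag-driven one. Those ranges rest on linearity, no delay, mono-exponential decline and adult half-lives, and the lower end is the least plausible. It would be wrong to conclude from them that a QTc effect is being hidden: the documents report none in healthy subjects, and other planned outputs use or can use the off-drug reference. The change is worth making because it is cheap and concerns a safety endpoint.

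**What to change.** In SAP 4.5:

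1. Add the change from study baseline (last value before first dose) at 2 h and 4 h post-dose for all quantitative ECG variables.
2. State that the QTcB and QTcF increase categories and the shift tables in the Week 1 and 12 analysis use study baseline.
3. Keep the pre-dose to post-dose change as a supportive summary.

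The cost is a few words and one more table. Protocol Table 4 already schedules the baseline ECG, so no new recordings are needed. A table note should say that the baseline ECG is not necessarily matched for time of day and may precede the post-dose ECGs by up to 12 weeks.
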